3 STUDY OBJECTIVES

3.1 Primary Objective

Perform quantitative analysis of the immunologic and genetic changes in immune cell populations in lesional and non-lesional skin after dupilumab treatment (15 AD patients) at weeks 2, 4, 12 compared to baseline week 0. The immunologic and genetic profiles in AD patients will also be compared to healthy control skin surgical discard specimens (n=15). The primary endpoint is the percent change from pre-treatment baseline of CD4+ T effector cells expressing IL-4 at weeks 2, 4, 12 in dupilumab-treated patients.

3.2 Secondary Objectives

Use RNA-seq to identify differentially expressed genes and pathways in each cell population at weeks 2, 4, 12 compared to pre-treatment baseline in dupilumab-treated patients. We will explore whether early molecular changes are predictive of the clinical response to dupilumab (reduction of EASI/IGA and improvement in pruritus score), which could lead to the identification of novel biomarkers. Microbiome samples from skin and stool at weeks 0, 2, 4, 12, and 52 will be banked for future analysis. Allergic contact dermatitis patch testing will be performed prior to and after 6 months of treatment with dupilumab to gain a better understanding of how dupilumab affects contact allergy.

4 STUDY DESIGN

4.1 Study Overview

This is a single center, open-label study. Fifteen subjects with moderate to severe AD will receive dupilumab for a treatment period of 52 weeks (i.e. last injection on week 48). Surgical discard specimens will also be collected from fifteen healthy subjects. Biopsy samples from AD subjects and surgical discard samples will undergo molecular profiling. Skin swabs and stool samples will be collected and banked for future analysis. **The reason to treat patients for 52 weeks is to have the ability to correlate early molecular events with clinical outcomes (EASI, IGA, itch score) at week 52. In addition, collection of microbiome samples will be performed at week 52.** See Flowchart for timeline of study activities.

5 CRITERIA FOR EVALUATION

5.1 Primary Analysis Endpoint

Percentage change from pre-treatment baseline of CD4+ T effector cells expressing IL-4 at weeks 2, 4, 12 in dupilumab-treated patients.

5.2 Secondary Analysis Endpoint

Number of differentially expressed genes and pathways in each cell population at weeks 2, 4, 12 compared to pre-treatment baseline using RNA-seq.

We will also explore whether early molecular changes are predictive of the clinical response to dupilumab at 52 weeks (reduction of EASI and improvement in pruritus score), which could lead to the identification of novel biomarkers.

5.3 Safety Evaluations

Safety and tolerability to dupilumab will be assessed by adverse events, vital signs, physical examinations (including skin examinations and injection-site evaluations), and concomitant medication review. Laboratory assessments will be performed at screening.

6 SUBJECT SELECTION

6.1 Study Population

Subjects with a diagnosis of moderate to severe atopic dermatitis for at least 3 years prior to enrollment who meet the inclusion and exclusion criteria will be eligible for participation in this study.

6.2 Inclusion Criteria

Inclusion criteria for AD subjects:

1. Ability to provide written informed consent and comply with the protocol.
2. At least 18 years of age.
3. Diagnosis of chronic atopic dermatitis for at least 3 years prior to enrollment.
4. Subject is considered a candidate for phototherapy or systemic therapy
5. Eczema Area and Severity Index (EASI) score ≥ 12
6. Investigator Global Assessment (IGA) ≥ 3
7. 10% body surface area (BSA) or greater
8. Subject is unlikely to conceive due to male, post-menopausal, or using adequate contraceptive (barrier, hormonal, implant, or permanent sterilization methods).
9. Physical exam within clinically acceptable limits.

Inclusion criteria for healthy controls obtained by surgeons (surgical specimens):

4. Sample of non-inflamed skin.
5. No history of autoimmune disease.
6. At least 18 years of age.

6.3 Exclusion Criteria

Exclusion criteria for AD subjects:

1. Subject is unable to provide written informed consent or comply with the protocol.
2. Subject is younger than 18 years of age.
3. Subject with mild atopic dermatitis (EASI<12 and IGA<3) or is not a candidate for phototherapy or systemic treatments.
4. Subject with current, or a history of, severe atopic dermatitis well controlled on current therapy.
5. Serious known infection.
6. History of immunosuppression (including human immunodeficiency virus (HIV)).
7. History of malignancy within 5 years before the screening visit, except completely treated in situ carcinoma of the cervix, completely treated and resolved non-metastatic squamous or basal cell carcinoma of the skin.
8. Severe concomitant illnesses.
9. Having used immunosuppressive/immunomodulating drugs (e.g., systemic corticosteroids, cyclosporine, mycophenolate-mofetil, IFN- γ , Janus kinase inhibitors, azathioprine, methotrexate, etc.) or phototherapy within 4 weeks before the baseline visit.
10. Treatment with topical corticosteroid or topical calcineurin inhibitor within 1 week

- before the baseline visit.
11. Treatment with any cell-depleting agents including but not limited to rituximab: within 6 months before the baseline visit, or until lymphocyte count returns to normal, whichever is longer, or use of other biologics: within 5 half-lives (if known) or 16 weeks prior to baseline visit, whichever is longer.
 12. Treatment with oral antibiotics within 2 weeks of the baseline visit.
 13. Physical exam not within clinically acceptable limits.
 14. Subjects possess other diagnoses that, in the investigator's opinion, preclude him/her from safely participating in this study or interfere with the evaluation of the subject's atopic dermatitis.
 15. Subjects possess other diagnoses that, in the investigator's opinion, preclude him/her from safely participating in this study or interfere with the evaluation of the subject's atopic dermatitis.
 16. History of known or suspected intolerance to any of the ingredients of the investigational study product.
 17. Pregnant or nursing (lactating) women, where pregnancy is defined as the state of a female after conception and until the termination of gestation, confirmed by a positive hCG laboratory test (>10 mIU/mL).
 18. Women of child-bearing potential, defined as all women physiologically capable of becoming pregnant, unwilling to use effective contraception during the study and for 6 weeks after stopping treatment. Effective contraception is defined as either:
 - Barrier method: Condom or occlusive cap (diaphragm or cervical/vault caps) with spermicide (where available). Spermicides alone are not a barrier method of contraception and should not be used alone.

The following methods are considered more effective than the barrier method and are also acceptable:

- Total abstinence: When this is in line with the preferred and usual lifestyle of the subject (Periodic abstinence [e.g. calendar, ovulation, symptothermal, post-ovulation methods] and withdrawal are not acceptable methods of contraception)
- Female sterilization: have had a surgical bilateral oophorectomy (with or without hysterectomy) or tubal ligation at least six weeks before taking study treatment. In case of oophorectomy alone, only when the reproductive status of the woman has been confirmed by follow up hormone level assessment.
- Male partner sterilization (at least 6 months prior to screening). For female subjects on the study, the vasectomized male partner should be the sole partner for that subject.
- Use of established oral, injected or implanted hormonal methods of contraception, intrauterine device (IUD) or intrauterine system (IUS)

NOTE: Women are considered post-menopausal and not of child bearing potential if they have had: 12 months of natural (spontaneous) amenorrhea with an appropriate clinical profile (e.g. age appropriate, history of vasomotor symptoms) or six months of

spontaneous amenorrhea with serum FSH levels >40 mIU/mL and estradiol <20 pg/mL or surgical bilateral oophorectomy (with or without hysterectomy) or tubal ligation at least six weeks before taking study treatment. In case of oophorectomy alone - only when the reproductive status of the woman has been confirmed.

Exclusion criteria for healthy controls obtained by surgeons (surgical specimens):

1. No areas of non-inflamed skin.
2. History of autoimmune disease.
3. Subject is younger than 18 years of age.

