1 BACKGROUND

Atopic dermatitis is a chronic, relapsing inflammatory skin disease characterized by intense pruritus and skin xerosis. Dupilumab is the first FDA-approved therapy for adult patients with moderate-to-severe atopic dermatitis in the class of recombinant high-affinity, fully human immunoglobulin-G4 (IgG4) monoclonal antibody that selectively targets the receptor alpha subunit of Interleukin-4 (IL-4). By binding to the IL-4 receptor alpha subunit, dupilumab modulates both the IL4 and Interleukin-13 (IL-13) pathways, which type 2/Th2 cytokines implicated in numerous allergic diseases. Through this blockade, dupilumab inhibits the inflammatory response that plays a role in the development of atopic dermatitis.

Non-clinical studies have not shown any impediment to using dupilumab administered subcutaneously in man.

The approval of dupilumab (Dupixent ®) was based on the safety and efficacy outcomes from 3 Phase III studies known as SOLO 1, SOLO 2, and CHRONOS. These trials included over 2,119 patients with moderate-to-severe atopic dermatitis not adequately controlled by topical medications.

For more detail refer to the Prescribing Information.

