7.2 Prohibited Medications and Treatments

The following are prohibited during the study and prior to the study for a set duration as follows:

- Systemic immunosuppressive or immunomodulatory treatments: 4 weeks.
- Phototherapy: 4 weeks.
- Cell-depleting agents including but not limited to rituximab: 6 months or until lymphocyte count returns to normal, whichever is longer.
- Biologics: 16 weeks or within 5 half-lives (if known), whichever is longer.
- Topical treatment that is likely to impact signs and symptoms of atopic dermatitis such as corticosteroids, vitamin D analogues, pimecrolimus, retinoids, salicylic acid, lactic acid, tacrolimus, tar, urea, α -hydroxy or fruit acids: 1 week.
- Live vaccinations: 6 weeks.
- Any investigational treatment or participation in any interventional trial: 4 weeks or 5 half-lives, whichever is longer.
- Any oral antibiotic: 2 weeks.
- Subjects will be asked to avoid bathing areas of microbiome skin swabbing for a 24 hour period prior to swabbing.

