9.2.6 Pre-treatment and post-treatment dupilumab testing

Pre-dupilumab patch testing:

Each of the 15 patients will be patch tested to a core series of allergens (see below). The allergens will be applied to the back of the patient using Finn Chambers (SmartPractice, Phoenix, AZ) on Scanpor tape (Norgesplaster Alpharma AS, Vennesla, Norway). More Scanpor tape will be applied over the patches to secure them to the back. 48 hours later the patient will return for patch removal and photography. Readings will be graded as follows: ? (weak/doubtful), + (mild), ++ (strong), or +++ (very strong) on the basis of degrees of induration, papules, vesicles, and/or spreading beyond the disc space. A final determination of “allergic/positive” or “not allergic” will be determined on the basis of the pattern (crescendo/decrescendo), patch test appearance, and known characteristics of that allergen. For example, a weak/doubtful (macular erythema) reaction to a formaldehyde-releasing agent could be determined to be an allergic/positive reaction in the setting of multiple or stronger reactions to related formaldehyde-releasing allergens. The clinical relevance of the positive patch test reaction will be determined using the patient’s history and clinical skin examination. Current relevance is defined as definite (a use test with the suspected item containing the putative allergen was positive, or a patch test to the object or product was positive), probable (the allergen can be verified as present in known skin contactants, and the clinical presentation was consistent), or possible (the patient is exposed to circumstances in which skin contact with materials known to contain the allergen was likely to occur). Past relevance will also be indicated. At the final visit the patient will be counseled regarding allergen avoidance.

Post-dupilumab patch testing:

After 6 months of dupilumab therapy the patient will undergo a second round of patch testing, to the same core series of allergens and using the same procedures described above. If new allergens are identified, additional avoidance counseling will occur.

Timing and logistics:

Each patch test will require 2 three-part patient visits. Application of allergens will take approximately 20 minutes. Removal and photography (48 hours later) approximately 10 minutes. Final reading (120 hours after placement) and allergen avoidance counseling will occur at the final visit (approximately 30 minutes).

ACD Core 80 Series

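### Prior dupilumab users can enrol after a biologic washout, so the baseline and the first patch test need not be dupilumab-naive

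*Combined protocol and SAP*

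**What the plan says.** The rule on earlier biologics is a washout. Section 6.3, item 11, after dealing with cell-depleting agents, excludes "use of other biologics: within 5 half-lives (if known) or 16 weeks prior to baseline visit, whichever is longer"; the synopsis carries the same rule as its exclusion item 13. Section 7.2 lists "Biologics: 16 weeks or within 5 half-lives (if known), whichever is longer". None of these names dupilumab.

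The one criterion that refers to the study product is about tolerance: "History of known or suspected intolerance to any of the ingredients of the investigational study product" (6.3, item 16). Item 4 of the same section reads "Subject with current, or a history of, severe atopic dermatitis well controlled on current therapy".

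The drug is already on the market for these patients. Section 1 says "Dupilumab is the first FDA-approved therapy for adult patients with moderate-to-severe atopic dermatitis", and 8.3 describes the trial regimen as the approved one.

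Section 5.1 defines the primary endpoint as "Percentage change from pre-treatment baseline of CD4+ T effector cells expressing IL-4 at weeks 2, 4, 12 in dupilumab-treated patients". Section 9.2.6 labels the first round of allergen testing "Pre-dupilumab patch testing". Sections 5.2 and 14.2 plan to explore whether early molecular change predicts clinical response at week 52. Section 10.1, item 5, records earlier treatments for the disease at screening, but nothing in section 14 uses that history.

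**The concern.** This is a single-arm mechanism study in 15 patients, and each patient's own week 0 sample is the reference. A patient who has had dupilumab before differs from a naive one in three ways that matter here.

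- **Molecular change.** The change from week 0 to weeks 2, 4 and 12 is a response to re-exposure. The documents give no evidence that skin T-cell populations return to the untreated state after the washout.
- **Prediction.** The patient and the investigator may already know how the patient responded last time. Enrolment could then be selective on something close to the outcome being predicted.
- **Contact allergy.** The before-and-on-drug comparison of patch tests loses its before.

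The healthy surgical specimens do not help. They come from untreated, de-identified donors and cannot separate first exposure from re-exposure.

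**Working it through.** **1. Does any rule keep a prior user out?**

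| Rule | Whom it stops | Whom it lets through |
|---|---|---|
| 6.3 item 11 and 7.2 (biologics) | Users inside the washout window | Anyone who stopped earlier |
| 6.3 item 16 (intolerance) | Known or suspected intolerance | Those who stopped for lack or loss of effect, or for another reason |
| 6.3 item 4 (well controlled) | Severe disease controlled on present treatment | Past responders who stopped and relapsed; past non-responders |
| 6.3 item 9 (immunomodulators "or phototherapy within 4 weeks before the baseline visit") | Recent users | Also only time-limited |
| 6.3 items 14 and 15 | Other diagnoses, at the investigator's discretion | Prior treatment is not a diagnosis |
| 6.2 items 5 to 7 (EASI at least 12, IGA at least 3, BSA at least 10%) | Inactive or mild disease | Relapsed or refractory prior users |

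The word other in item 11 can be read in two ways. Most naturally it means biologics other than cell-depleting agents, so dupilumab falls under the washout. If it means biologics other than the study drug, 6.3 places no limit on prior dupilumab and only 7.2 applies. On either reading a washed-out prior user is eligible.

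**2. Which analyses need a naive baseline?** Pre-treatment in 5.1 can be read as before study treatment (3.1 speaks of week 0), and in that sense it remains true of a prior user. The label in 9.2.6 cannot be read that way: for a prior user it is false. The prediction analysis lies in between. Its outcome is observed in this study, but past response may be known at entry.

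**3. Size for the primary t-test.** Inputs from 14.4: minimum relevant reduction 10%, SD of change 10%, so d = 10/10 = 1.00; alpha 0.05; power 0.80; n = 15 planned. Sidedness is not stated.

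*The plan's own figure (9 patients).*

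- Two-sided normal approximation: (1.960 + 0.842)² / 1.00² ≈ 7.85, rounded up to 8.
- With the small-sample correction: 7.85 + 1.960²/2 = 9.77, rounded up to 10.
- Exact t, two-sided: n = 10 (power 0.803; n = 9 gives 0.748).
- Exact t, one-sided: n = 8 (power 0.815; n = 9 gives 0.862).

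The stated 9 is within one patient of each, so it is reproduced closely enough.

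*At n = 15, all naive.* The noncentrality is d√n = 1.00 × √15 = 3.87 on 14 degrees of freedom, giving two-sided power 0.949.

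*With k prior users.* The documents give neither k nor the effect in prior users. Two assumed effects are shown: none, and half. The mean reduction is 10 − 10k/15 in the first case and 10 − 5k/15 in the second. Power comes from 200,000 simulated trials per row, with SD 10 within each group and a two-sided test at 0.05.

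| k | Share of 15 | Mean, no effect | Power | Mean, half effect | Power |
|---|---|---|---|---|---|
| 0 | 0% | 10.0 | 0.95 | 10.0 | 0.95 |
| 1 | 6.7% | 9.3 | 0.91 | 9.7 | 0.93 |
| 2 | 13.3% | 8.7 | 0.85 | 9.3 | 0.91 |
| 3 | 20.0% | 8.0 | 0.77 | 9.0 | 0.89 |
| 4 | 26.7% | 7.3 | 0.68 | 8.7 | 0.87 |
| 5 | 33.3% | 6.7 | 0.59 | 8.3 | 0.84 |

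The Monte Carlo standard error at 0.77 is √(0.77 × 0.23 / 200,000) ≈ 0.0009. Each figure is for one comparison with no dropout and no adjustment for the three time points or two skin types.

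**The case against.** The case for leaving the rule alone has substance.

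- Prior users may never enrol. Those who are intolerant or currently well controlled are already excluded, and entry requires active disease.
- The washout is the longer of two limits. The documents give no half-life, so carry-over cannot be quantified. A reader might infer that residual drug contaminates the baseline; nothing in the documents shows that.
- Relapsed past responders may respond again just as well, and past failures could shift results the other way.
- The prediction work is exploratory, and section 14 specifies no patch-test analysis.
- Earlier treatments are recorded at screening and a detailed SAP is still to be written, so a naive-only sensitivity analysis could be added without touching eligibility.

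The first three points mean that bias is possible but not demonstrated, and they rule out any firm estimate of its size. The fourth lowers the inferential stakes but does not remove the purpose: 4.1 gives correlation of early molecular events with week 52 outcome as a reason for treating for 52 weeks, and 3.2 makes the effect on contact allergy an objective. The fifth supplies a good fallback, but with 15 patients dropping two or three from an analysis is costly, whereas not enrolling them costs little.

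**Conclusion.** The gap is real. As written, the criteria admit washed-out, non-intolerant prior users of the study drug with active disease, and no planned analysis separates them.

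The patch-test comparison and the prediction of week 52 response are the most exposed, because there the problem is validity and not power. For the primary t-test the effect is modest. Under the illustrative assumptions, power falls below the planned 0.80 only when three or more of 15 are prior users with no response at all. With half the effect it stays at 0.84 or above for up to five.

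Three stronger conclusions might be inferred, and the documents support none of them:

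- **That the objectives are biased.** This would need prior users to enrol and either effects that outlast the washout or a re-exposure response unlike a first one. The documents are silent on each.
- **That the week 52 outcome is known in advance.** Only a past response may be known.
- **That 14.4 forecasts a 10% fall which prior users would erode.** The 10% is a minimum relevant effect, used here only as a yardstick.

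**What to change.** Add one exclusion to 6.3 and the synopsis: any prior treatment with dupilumab, at any time. Keep the existing washout for other biologics. The argument here is about the study drug itself and does not support a lifetime exclusion of every agent acting on IL-4 or IL-13.

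If a prior user is already enrolled, report the number from the treatment history recorded under 10.1, item 5. Specify in the SAP that the primary, prediction and patch-test comparisons will be repeated in dupilumab-naive patients as a sensitivity analysis.

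The cost is one line in an amendment and a somewhat smaller recruitment pool for 15 places. Section 2 reports more than 500 atopic dermatitis patients seen a year, but that counts all such patients and not those who meet the severity and clear-skin requirements, so the loss is probably small but cannot be calculated from the documents.

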7 CONCURRENT MEDICATIONS

7.1 Allowed Medications and Treatments

All prior concomitant medications must be on a stable dose for at least 4 weeks before the first study treatment administration. All subjects should be maintained on the same medications throughout the entire study period, as medically feasible. Any changes in medications and medication dosing will be recorded on the CRF. After the screening period, the use of concomitant medication for atopic dermatitis in all body regions is restricted to bland emollients and other non-medicated interventions.

7.2 Prohibited Medications and Treatments

The following are prohibited during the study and prior to the study for a set duration as follows:

- Systemic immunosuppressive or immunomodulatory treatments: 4 weeks.
- Phototherapy: 4 weeks.
- Cell-depleting agents including but not limited to rituximab: 6 months or until lymphocyte count returns to normal, whichever is longer.
- Biologics: 16 weeks or within 5 half-lives (if known), whichever is longer.
- Topical treatment that is likely to impact signs and symptoms of atopic dermatitis such as corticosteroids, vitamin D analogues, pimecrolimus, retinoids, salicylic acid, lactic acid, tacrolimus, tar, urea, α -hydroxy or fruit acids: 1 week.
- Live vaccinations: 6 weeks.
- Any investigational treatment or participation in any interventional trial: 4 weeks or 5 half-lives, whichever is longer.
- Any oral antibiotic: 2 weeks.
- Subjects will be asked to avoid bathing areas of microbiome skin swabbing for a 24 hour period prior to swabbing.

